It may be useful to include a brief synopsis of the study for quick reference. Complete information and, if required, add additional rows.

Study Title	Virtual Reality for Pain and Anxiety in Children
Internal ref. no. (or short title)	B00823
Study Design	Feasibility/Acceptability study
Study Participants	Children aged 5-13 years who require cannulation or venepuncture as an inpatient
Planned Size of Sample (if applicable)	32
Follow up duration (if applicable)	None
Planned Study Period	4 weeks
Research Question/Aim(s)	
 • Conduct initial acceptability/feasibility testing of VRH use with children undergoing venepuncture or cannulation in an acute, often unplanned inpatient setting in a children's hospital. • Assess level of child and parent reported pain during procedure as well as change in heart rate.

Virtual Reality for Pain and Anxiety in Children

	
 • Generate pilot data to design software and develop methods, outcome measures and patient/family engagement for a large randomised control trial (RCT) in the same setting to establish efficacy of VRH in reduction of perceived pain.
--	--

FUNDING AND SUPPORT IN KIND

FUNDER(S) (Names and contact details of ALL organisations providing funding and/or support in kind for this study)	FINANCIAL AND NON FINANCIAL SUPPORT GIVEN
Manchester University NHS Foundation Trust Contact details as above	£9380
VREvo Contact details as above	Non-financial advice and support given in planning of study and in use of Virtual Reality Headsets.

ROLE OF STUDY SPONSOR AND FUNDER

Manchester Foundation Trust are the main sponsor. They will have joint responsibility with the study team for the design, conduct and management of the study. The study team will perform data interpretation and analysis and then write the manuscript. They will take responsibility for submission of the manuscript for publication dissemination of results. They will take responsibility for the planning of follow up studies. They and not the funder will control all final decisions over the study.

VREvo are a Virtual Reality Education company part owned by the University of Manchester. They were involved in the planning of the study and will aid in the use of the technology during the study. They have provided training on how to use the technology. They will be involved in drafting the final manuscript and planning any follow up studies.

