4 RESEARCH QUESTION/AIM(S)

4.1 Objectives

1. Conduct initial acceptability/feasibility testing of VRH use with children undergoing venepuncture or cannulation in an acute, often unplanned inpatient setting in a children's hospital.
2. Assess level of child and parent reported pain during procedure as well as change in heart rate.
3. Generate pilot data to design software and develop methods, outcome measures and patient/family engagement for a large randomised control trial (RCT) in the same setting to establish efficacy of VRH in reduction of perceived pain.

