4.2 Outcome

1. Perceived and reported pain/anxiety scores for children undergoing venepuncture or cannulation with VRH.
2. Change in heart rate before, during and after painful procedure
3. Clinicians' feedback on the use of VRH in inpatient painful procedures

5 STUDY DESIGN and METHODS of DATA COLLECTION AND DATA ANALYSIS

Practitioners will be encouraged to contact the research team each time they are to perform a procedure between 0830H and 1600H and, unless already with another child using VRH, the research team will come to speak to parents to consent to the study. If consent is obtained then the procedure will be performed using current standard care as well as use of a VRH. The Oculus Go is a cheap and quick to set up headset. Off the shelf software will be selected that will distract but not require the movement of both arms. Software such as The Blu, Ocean Rift and Pet lab will be selected, dependent upon the age of the patient.

VRH will be brought to the room planned for procedure and set up for the child as part of the preparation for venepuncture/cannulation. Prior to application of VRH children will be asked to score their current pain score using the Wong Baker Faces Score (WBFS)¹. This will be transcribed by the researcher. VRH use will be commenced at least 3 minutes prior to commencement of painful procedure. The procedure will then be performed by the practitioner and VRH supervised by parent(s). The researcher will not participate in the procedure beyond initial setup of the VRH to ensure real world feasibility is being tested for. Once the procedure is completed, the child will be allowed to continue using the VRH while clinicians and parents involved in the procedure fill in the feedback forms.

Feedback forms for parents will focus on perceived pain score and short qualitative review regarding acceptability, whether they would consider repeat application at subsequent venepuncture procedures, if VRH was well tolerated and whether they felt it helped. Feedback from clinicians will focus on ease of use of VRH, if they felt it facilitated procedure or whether it was felt to prolong the procedure. Forms will be filled in by parents and clinicians themselves and then handed to the researcher.

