Children will then have the VRH removed and be asked to score their current pain again using the WBFS. Children's WBFS will be compared pre and post procedure. Assessment of acceptability/feasibility for children will be based on 3 **questions** – 1. Do they like it, 2. Was VRH wear comfortable and 3. Did they feel unwell whilst wearing VRH. Questionnaire answers will also be used to design future trials and bespoke VR software.

Questionnaires will then be pseudonymised and transcribed on to a secure computer for analysis of data. Interpretation of data will be performed by the clinical research team. Any statistical analysis required will be performed using SPSS Statistics 25 on pseudonymised datasets. Paper questionnaires will be kept in a locked drawer, in a locked room, on a locked research unit where access is only via swipe card. Access to paper questionnaires and digital data will only be for the immediate clinical research team of [name] and [name].

¹ Wong-Baker FACES Foundation (2018). Wong-Baker FACES® Pain Rating Scale. Retrieved [11/10/19] with permission from <http://www.WongBakerFACES.org>

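### Objective 2 is child-reported pain during the procedure, but Section 5 asks the child only for current pain before the headset goes on and after it comes off

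*Protocol*

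**What the plan says.** The Synopsis and Section 4.1 give the second objective as "Assess level of child and parent reported pain during procedure as well as change in heart rate". The third objective is to prepare methods and outcome measures for a randomised trial "to establish efficacy of VRH in reduction of perceived pain". Section 4.2 lists as its first outcome "Perceived and reported pain/anxiety scores for children undergoing venepuncture or cannulation with VRH", without saying when the scores are taken or what period they cover.

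Section 5 sets out what the child is asked and when:

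- Before the headset: "Prior to application of VRH children will be asked to score their current pain score using the Wong Baker Faces Score".
- After the procedure, "the child will be allowed to continue using the VRH while clinicians and parents involved in the procedure fill in the feedback forms".
- After that: "Children will then have the VRH removed and be asked to score their current pain again using the WBFS".
- The stated comparison is that the children's "WBFS will be compared pre and post procedure".
- Three further questions go to the child, on liking the headset, its comfort, and feeling unwell while wearing it.

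Parents give their own perceived pain score on a separate form.

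**The concern.** The objective concerns pain at the time of the needle. Both child ratings concern pain at the moment of asking. One precedes the headset. The other follows an interval of unstated length in which the child may still be distracted by the headset.

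Two things are at stake. First, the child part of Objective 2 would have no direct measurement. Second, the pre/post difference could be misread. If pain has faded by the second rating, a difference near zero is what one would see whether or not the headset helped, and it could be taken as a sign of benefit.

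This carries into Objective 3, because the pilot is meant to develop outcome measures for a trial of perceived pain and Section 5 says the questionnaire answers will inform future trials. A rating that was never taken cannot be recovered in the analysis.

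**Working it through.** The point rests on comparing passages of text. The protocol's one relevant statistical figure, the precision statement in Section 7.2.1, concerns acceptability. It reproduces: 24/32 = 75.0%, with exact limits Beta(0.025; 24, 9) = 56.60% and Beta(0.975; 25, 8) = 88.54%, against the stated 56.6-88.5%. It has no bearing on the pain rating.

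**Step 1: list every item Section 5 puts to the child.**

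| Item | When | What it refers to | Pain during procedure? |
|---|---|---|---|
| WBFS, first | Before headset | Current pain | No |
| WBFS, second | After procedure, adult forms and headset removal | Current pain | No |
| Liking | Time not stated | The headset | No |
| Comfort | Time not stated | The headset | No |
| Feeling unwell | Time not stated | Time wearing the headset | No |

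Count: 2 pain ratings + 3 acceptability questions = 5 items. Items on pain during the procedure: 0 of 2 pain ratings, 0 of 5 items.

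**Step 2: look for the measure elsewhere.** Outcome 1 in Section 4.2 names pain and anxiety scores but adds no rating and no time point. The parent's score is a proxy, and Objective 2 lists child and parent reports separately. Heart rate is to be followed before, during and after the procedure, so the protocol draws this distinction for heart rate but not for the child's pain. No other section supplies a child rating of pain during the procedure.

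**Step 3: see what the planned comparison can show.** Let B be the first current-pain rating, D the pain during the procedure and A the second current-pain rating. Objective 2 asks for the level of D. The planned comparison is A − B, in which D does not appear. Two children with the same B and A but very different D give the same result. A reflects D only so far as pain persists to the second rating, and the protocol gives neither the interval nor any pain figures from which to judge that.

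**Step 4: check early headset removal.** Section 8.1 has the headset taken off and not put back if the child is unwell or does not want it, and the procedure then continues without it. Section 5 ties the second rating to headset removal, so for these children the text does not fix when that rating is taken.

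**The case against.** The strongest reply is that the child questionnaire is not shown. Section 5 is a narrative of the visit, and its phrase for the second rating may be shorthand for an item worded differently on the form. That possibility stands, and it limits the finding to the protocol text. Even so, the text would need correcting to describe what is asked.

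It can also be said that a self-rating in the same session, after the needle, is child-reported pain around the procedure, and that the wait may be short because staying in the headset is optional. In part this holds: the study does collect child pain data, and how far the second rating falls short is unknown. But the objective says during, both ratings are worded as current, and no limit is set on the interval.

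The consequence for this study is modest. It is a single-arm feasibility study, acceptability is primary and sizes the sample, and no decision rule uses the WBFS. That is fair and bears on severity. It does not remove the link to Objective 3, which is to develop outcome measures for a trial of perceived pain.

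Finally, rewording Objective 2 would also remove the contradiction, and a recall question asked first could colour the current-pain rating that follows. Both are correct. Rewording leaves the study with no child rating of the needle pain. The order effect is avoided by asking current pain first.

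**Conclusion.** The concern holds. As Section 5 is written, none of the 2 child pain ratings and none of the 5 child items measures the quantity that Objective 2 names. The pre/post WBFS comparison describes current pain before the headset and residual pain afterwards. It may understate the pain of the procedure by an amount the protocol gives no means to estimate.

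This rests on two conditions: that the child questionnaire holds no item beyond those Section 5 describes, and, for the understatement only, that some pain has faded by the second rating.

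It should be fixed before recruitment. It does not threaten the primary outcome, the sample of 32, the parent's score or heart rate.

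**What to change.** Amend Section 5 at the point where the headset is removed and the second WBFS rating is taken. For a child whose headset came off early, use the end of the procedure.

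1. Ask current pain as planned. Straight afterwards, ask the child to rate on the WBFS how much it hurt during the procedure. This order keeps the second current-pain rating comparable with the first.
2. Name the rating of pain during the procedure as the child pain measure for Objective 2 and Outcome 1, and keep the pre/post current-pain comparison as secondary.
3. Record the time from the end of the procedure to the ratings.
4. If the child questionnaire already contains such an item, state this in Section 5 instead of adding one.

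The cost is one extra question, one recorded time, a small change to Section 5 and an amended child form. The child is already being asked for a rating then, and the rule in Section 5 that "The researcher will not participate in the procedure beyond initial setup of the VRH to ensure real world feasibility is being tested for" is respected. Headset delivery does not change. The drawback is reliance on recall over a short period, which the recorded time makes visible.

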7 SAMPLE AND RECRUITMENT

7.1 Eligibility Criteria

7.1.1 Inclusion criteria

Any child of age 5-12 years who are an inpatient in Royal Manchester Children's Hospital over a 4 week study period will be considered for consent if they require venepuncture or cannulation for a medical reason as determined by their lead medical team.

All individuals will be considered for inclusion in this study regardless of age, disability, gender reassignment, marriage and civil partnership, pregnancy and maternity, race, religion and belief, sex, and sexual orientation except where the study inclusion and exclusion criteria EXPLICITLY state otherwise.

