7.1.2 Exclusion criteria

Children under the age of 5 years (may not fit the headset, may become upset) and over the age of 12 years (pubertal, more mature understanding and expectations) will be excluded.

Children not needed venepuncture or cannulation will not be invited.

Children who have worn VRH previously and recognise dizziness/sickness or other ill health symptoms will not be asked to consent.

Parent/ guardians of children who are unsure about VRH will be excluded.

Parents will not be excluded if their first language is not English. As far as possible a translator will be arranged to translate child/parent responses and give feedback.

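### The child's question about feeling unwell in the headset has no pre-headset counterpart, so in ill inpatients the answer cannot separate existing symptoms from headset-induced ones

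*Protocol*

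**What the plan says.** **Who enters.** Under Section 7.1.1, inpatients aged 5-12 "will be considered for consent if they require venepuncture or cannulation for a medical reason as determined by their lead medical team". Section 7.2.1 intends the sample to span different degrees of underlying illness. The only exclusion in Section 7.1.2 that concerns symptoms looks back to earlier headset use: "Children who have worn VRH previously and recognise dizziness/sickness or other ill health symptoms will not be asked to consent". Current nausea, dizziness or malaise is not an exclusion.

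**What the child is asked before the headset.** Section 5: "Prior to application of VRH children will be asked to score their current pain score using the Wong Baker Faces Score". No other question to the child is described at that step.

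**What the child is asked afterwards.** The pain score is repeated, and "Children's WBFS will be compared pre and post procedure". Then: "Assessment of acceptability/feasibility for children will be based on 3" questions, covering liking, comfort and "3. Did they feel unwell whilst wearing VRH".

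**What else is collected or ruled out.** Parents report afterwards whether the headset was well tolerated and give a short qualitative review (Section 5). There is one group and no control. Section 8.6 says the research team will not look at the child's medical or surgical data. Section 8.8 says families cannot be contacted once data are acquired.

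**Where it is used.** Section 7.2.1 names acceptability of patient use as the primary outcome, with a 75% target in 32 children. Section 5 says questionnaire answers will help design future trials. Section 8.1 names dizziness and sickness as possible effects of the headset.

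**The concern.** Pain is read before and after, but the one unwanted effect that the Protocol itself anticipates is read only afterwards. As Section 5 describes it, question 3 is tied to the period of wearing. It does not ask about cause or about change from before. A child who felt sick from illness when the headset went on can truthfully answer yes, and so can a well child whom the headset made sick. The two answers look the same in the dataset.

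Two things are at stake. First, the share who felt unwell cannot be read as a headset effect when the answers are used to plan the later trial. This holds however the three questions are combined. Second, if an unwell answer counts against acceptability, the share set against the 75% target may be low for reasons unrelated to the headset. This depends on a scoring rule that the Protocol does not give.

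The gap lies in data collection. A statistical analysis plan can define a scoring rule, but it cannot recover a baseline answer that was never asked for.

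**Working it through.** **1. The plan's own figure.** Target 75% of 32 = 24 children. Exact two-sided 95% limits: lower = 2.5% quantile of Beta(24, 9) = 56.595%; upper = 97.5% quantile of Beta(25, 8) = 88.538%. This is 56.6-88.5%, as Section 7.2.1 states. The figure is correct and is not disputed.

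**2. Pain and feeling unwell side by side (Section 5).**

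| | Before headset | After headset | Planned comparison |
|---|---|---|---|
| Pain (WBFS) | asked | asked | pre against post |
| Feeling unwell | not described | asked once | none described |

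Other sources that might supply the missing cell: a control group (none), medical data (not reviewed, Section 8.6), later contact with families (not possible, Section 8.8), and the parents' tolerability report. Only the last exists. It is specific to the headset, but it comes from the parent and is also given once, afterwards.

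**3. Illustrative size for question 3 alone.** Inputs, all assumed because the documents give none of them:
- b = share already unwell before the headset: 10%, 30%, 50%
- h = share made unwell by the headset: 5%
- every child already unwell answers yes.

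If b and h are independent, share answering no = (1 - b)(1 - h). If they overlap fully, so that the same children are affected, share answering no = 1 - max(b, h).

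| b | Independent | Full overlap |
|---|---|---|
| 10% | 0.90 x 0.95 = 85.5% | 1 - 0.10 = 90% |
| 30% | 0.70 x 0.95 = 66.5% | 1 - 0.30 = 70% |
| 50% | 0.50 x 0.95 = 47.5% | 1 - 0.50 = 50% |

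The prior-unwell share at which the 'no' answers fall to 75% is 1 - 0.75/0.95 = 21% under independence and 1 - 0.75 = 25% under full overlap.

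**4. Illustrative effect on the 75% target.** Assume further that any unwell answer makes a child a non-acceptor, that true acceptability of the headset is 85%, and that prior illness is independent of it. Measured acceptability m = 0.85 x (1 - b). The chance of at least 24 acceptors is the upper tail of Binomial(32, m).

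| b | m | Chance of at least 24 of 32 |
|---|---|---|
| 0% | 85.0% | 0.96 |
| 5% | 80.8% | 0.85 |
| 10% | 76.5% | 0.67 |
| 20% | 68.0% | 0.26 |
| 30% | 59.5% | 0.05 |

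If instead the children already unwell fall as far as possible among the 15% who would not accept anyway, m = 1 - max(b, 0.15): 85% at b = 5% and 10%, 80% at 20%, 70% at 30%. The overlap therefore matters as much as the rate, and the documents fix neither.

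**The case against.** The strongest reply is that no bias in the primary outcome has been shown. A reader might infer that illness symptoms are in fact counted against the headset in the 75% figure. The Protocol does not support that. It says acceptability is based on three questions, but not how they combine or what makes a child an acceptor. Such a rule may properly sit in an analysis plan that is not shown. If acceptability rests mainly on liking, or the items are reported separately, the effect on the target disappears. This part of the objection stands.

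A reader might also take the 85.5%, 66.5% and 47.5% as the most that could answer no. They are not upper limits. Full overlap gives higher values, and so would children who answer about the headset rather than their illness, or who feel better while distracted.

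Three further points carry some weight:
- The child's questionnaire is not shown, and Section 5 may only summarise its wording.
- Parents know how the child was beforehand, so their tolerability report is useful evidence.
- A side-effect rate is not a listed outcome in Section 4.2, and a child who feels unwell in the headset for any reason bears on its use on the ward.

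These narrow the concern without removing it. The parents' view cannot be set against a baseline answer from the child, and Section 5 does say the answers will inform future trials. For that purpose, an item that mixes two causes is weak.

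**Conclusion.** The point holds in a limited form. Followed as written, Section 5 yields a tolerability item that cannot separate existing illness symptoms from headset-induced ones, and no later analysis can repair this. The parents' report helps only in part. That conclusion needs no numerical assumption.

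Understatement of acceptability against the 75% target is possible but conditional. It needs an unwell answer to count against acceptability, which the Protocol does not state, and a material share of children already unwell, which the documents do not give. The ranges shown also assume 5% headset sickness, a yes from every child already unwell, and either independence or full overlap. They show that the effect could run from negligible to large; they do not estimate it. The sample size and its stated interval are unaffected. This is a cheap improvement to data collection. It is neither a contradiction nor a wrong figure.

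**What to change.** In Section 5:
- At the existing pre-headset WBFS step, add one yes/no question to the child, for example: 'Do you feel dizzy, sick or unwell now?'
- Word question 3 comparatively, for example: 'While wearing the headset, did you feel dizzy, sick or more unwell than before?'
- Report symptoms that are new or worse than the pre-headset answer separately from those already present.

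The cost is one short question at a contact where the researcher already records a pain score, plus one reworded item. It needs no extra visit, staff or children, and it changes no eligibility or headset-removal rule.

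There are two downsides. Asking beforehand may prompt some children to notice or report symptoms. The change also does not separate unwellness caused by the needle procedure itself, which takes place while the headset is worn; that would need a control group.
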